11.1 Success of enrolment and follow-up

All registered participants and the success of their follow-up will be described in a flow chart (Figure 1). For additional information drop-out rate between groups will be tested with Fisher's exact test and baseline characteristics of drop-outs compared to those who completed the study will be tested with t-test or chi square. P-values for these tests will be shown in the text.

11.2 Baseline information

Participant characteristics at enrollment will be tabulated by treatment arms as indicated in tables 1a and 1b. Hypothesis testing will be performed for baseline information to give additional information but p-values will not be presented in Table 1 of the eventual manuscript. Methods used for hypothesis testing are indicated in Tables 1a and 1b.

11.3 Comparison of the change in length-for-age Z-score between intervention groups versus the control group

Box-whisker plots of the change in LAZ of all 6 groups will be shown side by side in Figure 2. The group means and standard deviations for the change in length (in cm) and LAZ (in z-score units) will be presented as indicated in Table 2. The table will also tabulate the difference in mean length and LAZ and their 95% confidence intervals between the control group and each of the intervention groups.

Mean change in LAZ in each of the intervention groups will be individually compared against that of the control group using a two-sample t-test. The Holm's method will be used to adjust for the multiple comparisons (Aickin & Gensler, 1996). The raw P-values are presented in tables but the text and conclusion will be based on the Holm-adjusted P-values.

The null-hypothesis of LNS having no impact on linear growth is rejected for each comparison that yields a Holm's adjusted p-value <0.05.

11.4 Comparison of milk-containing and milk-free LNS

This analysis will exclude participants who received no intervention or 10 g / day milkcontaining LNS. An ordinary least-square regression of the following form will be estimated:

$$\hat{y}_{i} = b_{0} + b_{1}D_{i} + b_{2}S_{i} + b_{3}(D_{i} \times S_{i})$$

where D=0 or 1 for the 20g and 40g group, respectively, and S=0 or 1 for the milk and milkfree LNS group, respectively. If the coefficient b3 for the interaction term does not reach a significance level of P<0.10, a simpler model without the interaction term will be estimated. 90% CI will be provided for each parameter. Ninety per cent instead of 95% CI is used because the non-inferiority consideration is one-sided and the use of 90% CI is the convention in this setting (Senn, 1997). Both models will be shown in table 3. Conclusion is to be based on the simpler model if the interaction term is not statistically significant (P>0.10), or vice versa.

Evaluation

The set non-inferiority margin for this analysis will be 0.15 Z-score units. If the lower bound of the 90% CI of the coefficient b2 is larger than -0.15, non-inferiority is confirmed. If the upper bound of the 90% CI is smaller than -0.15, inferiority is confirmed. If the upper and lower bounds of the 90% CI are larger and smaller, respectively, than -0.15, the finding is not conclusive.

If there is no significant interaction, the above evaluation only need be done once using the simple regression model without interaction. If there is significant interaction (P<0.10), the above evaluation will be done twice based on the model with interaction: Firstly on the 90% CI of the b2 coefficient concerning the non-inferiority of milk-free LNS in the 20g dose. Secondly on the 90% CI of the (b2+b3), obtained by the linearly combination command (Stata's **lincom**), concerning the non-inferiority of milk-free LNS in the 40g group.

11.5 Safety profile: Analysis of serious adverse events

The total number of serious adverse events (SAEs) will be presented by intervention group and SAE categorization, as indicated in Table 4. There will also be an analysis on the proportion of participants with at least one episode of SAE. For each of the intervention groups, the proportion and a relative risk (as compared to the control) will be presented as indicated in table 4. Fisher's exact test will be used to test the global null hypothesis of no differences between groups and the null hypothesis will be rejected if P<0.05. If the global null hypothesis is rejected, comparison between each intervention group and the control group will be conducted using log-binomial regression. Rate ratios (95% CI) for the incidence of any SAE will be calculated for each intervention group (as compared to the control group).

AE information was not collected after the participants had finished the intervention and completed the primary outcome study visit at 18 months of age.

Cumulative incidence curve for mortality will be presented graphically by intervention group as illustrated in Figure 3. The log-rank test will be used for testing global hypothesis and pair-wise comparisons. Hypothesis of equality of survivor functions is rejected if P<0.05. Hazard ratios and their confidence intervals will be estimated by the Cox regression model. The **sts** and **stcox** commands will be used.

12 General notes on statistical methods

12.1 Software

All analyses will be done in Stata version 12. The WHO 2006 multi-centre growth standard will be used for age-and-sex standardization of weight, length (height), weight-for-height, MUAC and head circumference.

12.2 Preparing anthropometric data for analysis

All the anthropometric measurements were completed in triplicate during each study visit. But for the analysis, the team will use the mean of the first two readings if they do not differ more than by a pre-specified tolerance limit. If they do, the third measurement will be compared with the first and second measurements and the pair of measurements that has smaller difference will be used to calculate the mean which will be used in analyses. If there are only one or two repeated measurements mean of those two will be used for the analyses.

The agreed tolerance limits between the first two measurements are:

- 1. length/height ≤ 0.5 cm
- 2. circumferences (head, MUAC) ≤ 0.5 cm
- 3. infant/child weight ≤ 0.1 kg
- 4. adult weight ≤ 0.1 kg
- 5. skinfold thickness $\leq 2.0 \text{ mm}$

The length, circumference and skinfold thickness measurements were recorded to last complete unit (mm). To account for the bias of always rounding the values a bit downwards, half a unit will be added to all length, circumference and skinfold thickness measurements prior to the analysis. This procedure is not done for weight measurements, since they were recorded accurately with electronic scales.

Missing growth values will be treated as missing, i.e. there will be no growth data imputation from the other data. Imputation is considered unreliable due to long time-interval between anthropometric measurements, at an age when growth faltering is common.

When measuring change in anthropometric values between two time intervals, the change will be treated as missing if there is a missing value in either of the respective time points.

12.3 Multiple comparisons

The study involves multiple objectives and therefore multiple sets of hypothesis. Statistically, the different sets of hypotheses are considered independent families of hypotheses. Statistical adjustment for multiple comparisons in one family of hypotheses does not need to consider the other families.

For efficacy analysis, each family consists of 5 hypotheses, each comparing an intervention group versus the control group. The Holm's adjustment method is used.

For safety analysis, it is preferable to err on the cautious side (Nauta, 2010). We began with testing the global null hypothesis of no difference between groups. If the global null hypothesis is rejected, raw P-values are used in the comparisons between intervention and control groups.

12.4 Confidence intervals

Regardless of results in hypothesis testing, the calculated ratios and differences in between-group comparisons will be complemented with confidence intervals (usually at 95% level but 90% for non-inferiority studies), for descriptive purpose. For the quantitative outcomes, confidence intervals will be based on t-test. For binary outcomes, the confidence intervals will be based on binomial distribution.

12.5 Interaction and effect modification

There will be two sets of test for interaction between the intervention group and selected other variables on their association with the primary outcome (change in length-for-age z-score). All tests will be done using the likelihood ratio test.

The first set of analyses will be hypothesis-driven and will include unambiguous predefined variables that could logically modify the effect of the nutritional intervention on infancy and early childhood growth. Variables included (as continuous variables where possible) in this analysis include:

- 1. The participant's baseline length-for-age (below / above median)
- 2. Maternal BMI at enrolment
- 3. Maternal height
- 4. Maternal age
- 5. Maternal parity
- 6. The participant's sex
- 7. Number of under-five year old children in the household
- 8. Cohabitation of the child's father with the rest of the family (yes / no)

9. Household food security

The second set of analyses will be exploratory in nature and will include variables that can be constructed in several ways or that cannot a priori be logically linked to an effect modification. Themes or variables included in this analysis include:

- 1. Maternal knowledge, attitudes, and practices around child nutrition
- 2. Household wealth

If a statistically significant interaction (p<0.1) is found, the outcome analysis will be completed as stratified by the respective predictor variable. Variables that show no interaction with the intervention group can be used as covariates in the main analysis.

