The iLiNS-DOSE trial was designed to study the impact of a 12-month LNS provision to infants and young children on their growth, nutritional status and a number of other health outcomes. For this purpose, a total of 1932 infants were enrolled in rural Malawi, randomized to receive for 12 months either no supplement or one of five alternative LNS-preparations (six study groups in total), and intensely monitored for 12-months for a large number of outcomes. Key details of the trial have been recorded at the clinical trial registry at the National Institutes of Health (USA) (www.clinicaltrials.gov), under the registration number NCT00945698. A full trial protocol is available from the contact person to this document.

This document (called "the statistical analysis plan" or SAP) describes the study group's plan for data analysis, management, and storage. The SAP is designed to be evolving over time. Version 1.0 documents the details of the hypothesis testing and other analyses on primary and selected secondary outcomes. Subsequent versions of the SAP will give further details on the analyses and hypothesis testing of additional secondary outcome variables and exploratory analyses from the data.

3 Study objectives

The main aim of the trial is to assess the safety and impact of LNS supplementation on linear growth of infants and young children and to identify individual, household, and village-level characteristics that would modify the effects of LNS on child growth. A secondary aim is to similarly study the impact of LNS on various other (secondary) outcomes in the same target group. Finally, the trial aims to provide descriptive information on issues that might be necessary to facilitate future demand creation for LNS interventions.

The above aims have been broken down into the following first five objectives that were predefined in the trial protocol. The safety aim was not explicitly stated among the predefined objectives in the trial protocol, but was listed under the primary outcomes for analysis.

- 1. To determine the lowest daily dose of LNS that will promote linear growth among 6-18 months old infants in a rural Malawian community with poor food security. *This covers also the objective to study if ANY dose of LNS promotes linear growth among the target group.*

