12.6 Covariate adjustment

The final decision on the use of covariates in main analyses will be decided based on preliminary analyses on the final dataset that includes information on the clustering of participants in the same group but does not provide information on the actual intervention delivered to each group.

At this stage, four different regression models for change in LAZ will be constructed, first of these with no covariate adjustments and models 2-4 with various adjustments. If the pointestimates for the regression co-efficient for the intervention group differ in any of the models by more than 10% from that in the unadjusted analyses, the adjusted analysis will be primarily presented in the eventual publications. If all the differences are smaller than 10% (Maldonado & Greenland, 1993), the results in the tables will be shown without covariate adjustments, but model 4 results will be provided in the text as supplementary information.

The four models include:

- 1. No covariate adjustment
- 2. Adjustment for baseline LAZ-score
- 3. Adjustment for baseline WHZ-score
- 4. Adjustment for baseline LAZ-score and baseline WHZ-score and for any of the variables presented in tables 1a and 1b showing statistically significant association (at p<0.1 level) with the change in LAZ-score

13 Storage and release of data

The data meta-data will be stored in a tailor-made hierarchical database, consisting of a MS Access front-end and MySQL tables in the back-end. The database, associated metadata, and form –specific do-files that contain all cumulative data corrections for the respective data collection forms are stored at a computer server at the University of Tampere and daily copied to

a server at the Mangochi research site, University of Malawi. A study statistician ([name]) acts as the manager for these data.

When an investigator wishes to perform certain analyses, s/he will request the respective data from the above-indicated data manager. The data manager will export all the data from the respective data collection form into an excel or Stata file, run the cumulative data correction do-file and then provide the corrected data, together with the syntax for the correction do file (that documents all the completed data editions) to the person requesting the data.

The databases and the do-files will be named with systematic naming format and stored at the central server at the University of Tampere. For each article, the following files will be stored:

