7.6 Interaction and effect modification

The following variables will be tested for interaction between the intervention group and the primary outcome (mean vector magnitude accelerometer counts). All tests will be done using the likelihood ratio test. The variables tested could logically modify the effect of the nutritional intervention on infancy and physical activity. Variables included (as continuous variables where possible) in this analysis include:

- 1. The participant's baseline length-for-age (below / above sample median) at 6 months
- 2. The participant's baseline weight-for-length (below/above sample median) at 6 months
- 3. The participant's sex
- 4. Season of participant's birth
- 5. Maternal education
- 6. Maternal age
- 7. Household food security

If a statistically significant interaction (p<0.1) is found, the outcome analysis will be completed as stratified by the respective predictor variable.

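### Baseline length-for-age is split at the median for the effect-modifier analysis, although SAP section 12.5 asks for continuous variables where possible; Appendix 4 does the same and adds weight-for-length

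*SAP*

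**What the plan says.** Section 12.5 of the SAP plans two sets of interaction tests on the change in LAZ. On the first set it says: "The first set of analyses will be hypothesis-driven and will include unambiguous predefined variables". The coding rule for that set is "Variables included (as continuous variables where possible) in this analysis include". Nine variables follow, and the first is "The participant's baseline length-for-age (below / above median"). On the method it says "All tests will be done using the likelihood ratio test". The consequence is set by the clause "If a statistically significant interaction (p<0.1) is found": the outcome analysis is then stratified by that variable. Variables without an interaction may serve as covariates in the main analysis.

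Appendix 4 (physical activity), section 7.6, uses the same lead-in and lists "The participant's baseline length-for-age (below / above sample median) at 6 months". Its second item treats baseline weight-for-length in the same way.

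Elsewhere the SAP handles baseline LAZ as a score. Section 7 calculates LAZ to two decimals. Model 2 in section 12.6 is "Adjustment for baseline LAZ-score", and model 4 includes the same score. Appendix 5 (sections 5.5 and 5.6) and Appendix 8 (section 10.4) list the baseline length-for-age z-score as a candidate modifier without any split.

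**The concern.** The item departs from the rule printed directly above it. A continuous coding is plainly possible, and the SAP does not explain the exception. Among the measured scales in the section 12.5 list, this is the only one with a cut: maternal BMI, height and age have none.

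Identifying characteristics that modify the effect of LNS is part of the main aim in section 3 and is objective 5. The test result also decides what happens next. In section 12.5 it determines whether the outcome is analysed in strata. In Appendix 4, section 7.7, a variable found to be a modifier leaves the adjusted model. A test with avoidably low power makes it easier to miss a real modifier. The main SAP's choice also spreads, because Appendix 1 (section 7.5) takes over its interaction plan and Appendix 2 (section 6.5) its list of factors.

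**Working it through.** The SAP gives no power or information figure for any interaction test, so there is none to reproduce. The size has to be worked out under stated assumptions.

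**Inputs from the SAP.** There are six groups; "a total of 1932 infants were enrolled in rural Malawi" (section 2), or 1932/6 = 322 per group if equal. The test is a likelihood-ratio test at p<0.10. Six groups by one modifier term give 5 degrees of freedom.

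**Assumptions not in the SAP.** Modification is linear in baseline LAZ; the shape of the LAZ distribution is varied below; residual SD is 1; the slope differs from control by the same amount in all five LNS groups.

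**Step 1: information kept by the split.** Under a linear effect, the share kept is the squared correlation between the modifier X and the indicator that X exceeds its median. For normal X this is 2/π = 0.637, so the loss is 1 − 0.637 = 36.3% (36.4% by simulation with 2,000,000 draws). In sample-size terms, 1932 × 0.637 ≈ 1230 children, and matching the continuous test would need π/2 = 1.57 times as many. For other shapes:

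| Shape of X | Loss |
|---|---|
| Uniform | 25% |
| Normal | 36% |
| Mildly skewed (skew-normal) | 38% |
| t, 5 df | 46% |
| Laplace | 50% |
| Exponential | 52% |

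**Step 2: illustration from an assumed 80% power.** The critical value of chi-square on 5 df at 0.10 is 9.24. A noncentrality of 10.45 gives 80.0% power. Multiplying it by the share kept:

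- normal: 10.45 × 0.637 = 6.65, power 60.5%
- uniform: 10.45 × 0.75 = 7.84, power about 68%
- exponential: 10.45 × 0.48 = 5.02, power about 49%

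**Step 3: dependence on the starting point.** With normal LAZ and slope difference s per SD of baseline LAZ, the noncentrality is 1932 × (1/6) × (5/6) × s². For s = 0.20 this is 10.73, and 6.83 after the split.

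| s | Continuous | Median split | Loss in points |
|---|---|---|---|
| 0.10 | 0.31 | 0.23 | 8 |
| 0.15 | 0.56 | 0.40 | 16 |
| 0.20 | 0.81 | 0.62 | 19 |
| 0.25 | 0.95 | 0.81 | 14 |

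Simulation with 1500 runs per case agrees: 0.82 against 0.63 at s = 0.20.

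**Step 4: checks in the other direction.** With no interaction, the simulated rejection rates were 0.09 (continuous) and 0.11 (split). With 1500 runs the standard error is √(0.1 × 0.9/1500) ≈ 0.008, so both are compatible with the nominal 0.10. With a step exactly at the median (effect +0.20 above and −0.20 below, in residual SDs), the split was the better test: 0.79 against 0.62.

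**The case against.** **The parenthesis may only define strata.** A significant interaction leads to stratified analysis, and stratifying a continuous variable needs a cut. The median might therefore be the stratum boundary, with the test itself continuous as the lead-in says. This reading is possible but less natural. The parenthesis on item 8 (father's cohabitation, yes / no) gives the coding of the variable, and no other measured scale in the list has a cut although each could equally need strata. The ambiguity is itself a reason to reword.

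**A prespecified exception is a legitimate choice.** A median fixed in advance prevents searching for a cut-point and gives balanced strata. That is true, but a continuous test needs no cut-point, and Appendix 5, section 5.4, follows up interactions with separate regression lines or adjusted means at key covariate values.

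**The loss is conditional.** This stands. Linearity and normality are assumptions, the 80% starting power is chosen for illustration and lies near the largest loss in Step 3, and a step at the median reverses the ranking. The SAP proposes neither a linear nor a step effect.

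**Stronger readings to avoid.** A reader might infer that baseline LAZ is the leading or most plausible modifier; the SAP lists nine without ranking them, and this one merely comes first. A reader might also take 36% as a fixed loss in this trial; the figure is not in the SAP and holds only under the assumptions above. Nor does the point reach the primary analysis, whose group comparisons are t-tests with Holm adjustment (section 11.3), or the covariate models, which already use the LAZ score.

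**Conclusion.** The inconsistency is real: section 12.5 and Appendix 4, section 7.6, depart without explanation from their own rule for variables that exist as z-scores. Read as the test coding, the split costs about 36% of the information on linear modification if the modifier is normal, and 25% to 52% across the other shapes tried. The fall from an assumed 80% power to about 60% (68% to 49% across shapes) shows the scale and does not estimate this trial's power. The effect is confined to the power of one of nine interaction tests in section 12.5 and two in Appendix 4, and to appendices that inherit the coding. This is a low-severity point, worth making because the correction is cheap and serves a stated aim.

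**What to change.** In section 12.5, state that the likelihood-ratio interaction test uses baseline LAZ as a continuous z-score, and that the below/above-median grouping is used only to present stratified results if an interaction is found. Say there that the median is the sample median, as Appendix 4 does. Make the same change in Appendix 4, section 7.6, for baseline LAZ and weight-for-length z-score. If the investigators intend the split as the test coding because they expect a step in the effect, they should say so and give the reason.

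The cost is SAP wording and one changed term per model; no new data are needed. The one downside is lower power if the effect really is a step near the median.

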12.6 Covariate adjustment

The final decision on the use of covariates in main analyses will be decided based on preliminary analyses on the final dataset that includes information on the clustering of participants in the same group but does not provide information on the actual intervention delivered to each group.

At this stage, four different regression models for change in LAZ will be constructed, first of these with no covariate adjustments and models 2-4 with various adjustments. If the pointestimates for the regression co-efficient for the intervention group differ in any of the models by more than 10% from that in the unadjusted analyses, the adjusted analysis will be primarily presented in the eventual publications. If all the differences are smaller than 10% (Maldonado & Greenland, 1993), the results in the tables will be shown without covariate adjustments, but model 4 results will be provided in the text as supplementary information.

The four models include:

- 1. No covariate adjustment
- 2. Adjustment for baseline LAZ-score
- 3. Adjustment for baseline WHZ-score
- 4. Adjustment for baseline LAZ-score and baseline WHZ-score and for any of the variables presented in tables 1a and 1b showing statistically significant association (at p<0.1 level) with the change in LAZ-score

13 Storage and release of data

The data meta-data will be stored in a tailor-made hierarchical database, consisting of a MS Access front-end and MySQL tables in the back-end. The database, associated metadata, and form –specific do-files that contain all cumulative data corrections for the respective data collection forms are stored at a computer server at the University of Tampere and daily copied to

a server at the Mangochi research site, University of Malawi. A study statistician ([name]) acts as the manager for these data.

When an investigator wishes to perform certain analyses, s/he will request the respective data from the above-indicated data manager. The data manager will export all the data from the respective data collection form into an excel or Stata file, run the cumulative data correction do-file and then provide the corrected data, together with the syntax for the correction do file (that documents all the completed data editions) to the person requesting the data.

The databases and the do-files will be named with systematic naming format and stored at the central server at the University of Tampere. For each article, the following files will be stored:

- 1. The database from which the analyses were performed
- 2. The data dictionary
- 3. The data correction do file(s)
- 4. The data analysis do file(s)
- 5. The actual scientific article

The data collection forms and respective user guides will be stored at the central study repository, in the computer server at the University of Tampere

In the longer run, there is a plan to place the data publicly available in the internet.

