- Objective 2 / hypothesis 2: The change in mean LAZ of infants receiving 20 or 40 g/day of LNS without milk from 6 to 18 months of age will not be lower than that of infants receiving a comparable intervention with milk-containing LNS.

6 Data cleaning and procedures on breaking the intervention code

The study group will adopt the following procedures for data cleaning and breaking the intervention code

- 1. In the first phase, a number of investigators will do preliminary cleaning of the data required to the main analyses (safety and linear growth outcomes). At this point, all investigators are totally blinded to the intervention each participant has been receiving.
- 2. A study statistician ([name]) makes a preliminary database that contains semi-clean data required for the main analyses. The database and summary statistics for each variable are distributed to the principal investigators, the members of the board governing trial implementation and the principal biostatistician for the trial. Once these individuals agree that the data are sufficiently comprehensive and clean, the study statisticians ([name], [name], and [name]) are provided with the database and a code that can be used to group the participants who received the same intervention together i.e. that gives group codes 1, 2, 3, 4, 5, and 6 without indicating the actual intervention each group number relates to.
- 3. The study statisticians review the data and complete preliminary analyses for group comparisons (without knowing the actual interventions). Based on these analyses, the study statisticians make suggestions for the amendment of the SAP (e.g. on the treatment of missing values). The investigators listed under 2) above then agree on a revised version of the SAP, after which the intervention code is broken and the main analyses are completed.
- 4. For secondary outcomes, the analyses will be mostly completed by investigators who are not study statisticians. For each of these analyses, data cleaning will be completed as above. Once the analyst has completed the first round of data cleaning without any knowledge about the group information, s/he will request scrambled group information from the

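### The primary growth test is not fixed: section 12.6 replaces the t-test of 11.3 through a 10%-change rule that reacts to chance imbalance when effects are near zero, and does not name the adjusted model that takes over

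*SAP*

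**What the plan says.** Section 11.3 of the SAP names the primary test: "Mean change in LAZ in each of the intervention groups will be individually compared against that of the control group using a two-sample t-test". Conclusions use Holm's method, and the null hypothesis is "rejected for each comparison that yields a Holm's adjusted p-value <0.05". Section 12.3 confirms that "each family consists of 5 hypotheses, each comparing an intervention group versus the control group".

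Section 12.6 then reopens the choice: "The final decision on the use of covariates in main analyses will be decided based on preliminary analyses on the final dataset", a dataset in which children are grouped by code but the interventions are not identified. Four regressions of change in LAZ are fitted:

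1. no covariates
2. baseline LAZ
3. baseline weight-for-length Z (WHZ)
4. both, plus any variable of Tables 1a and 1b associated with the outcome at p<0.1

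If the estimates "differ in any of the models by more than 10% from that in the unadjusted analyses, the adjusted analysis will be primarily presented". If not, the tables stay unadjusted and model 4 goes into the text.

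This happens at section 6, step 3: "The study statisticians review the data and complete preliminary analyses for group comparisons (without knowing the actual interventions"). The codes are numbers 1 to 6. Amendments to the SAP are agreed after this step, and only then is the code broken.

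**The concern.** Section 11.3 reads as a fixed primary test, yet 12.6 can displace it, and the rule in 12.6 is incomplete in three ways.

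- **Which model.** Models 2, 3 and 4 are all adjusted analyses. Model 4 is singled out only for the case in which the rule does not fire.
- **Which coefficient.** There are five contrasts, but 12.6 speaks of a single coefficient for the intervention group.
- **Which reference.** Coefficients against control require control to be known. Under codes 1 to 6 it is not, so the answer depends on which code serves as reference.

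The criterion also does not suit the design. Change-in-estimate is a way to look for confounding. Under randomisation any shift is chance imbalance, and its absolute size does not shrink with the treatment effect. A threshold relative to the effect is therefore easily crossed when the effect is small.

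At stake is which p-values enter Holm's procedure. Other parts inherit the rule: Appendix 1 (section 7.6) adopts it for secondary growth outcomes, and Appendix 2 (section 6.6) adopts it with three models. Appendices 4 and 8, by contrast, fix an unadjusted main analysis in advance.

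**Working it through.** **Inputs from the SAP.** "a total of 1932 infants were enrolled in rural Malawi" in six groups, so 1932/6 = 322 per group if allocation is equal (assumed). There are five contrasts, Holm at 0.05 and a 10% threshold. The only LAZ difference given a scale is the 0.15 Z non-inferiority margin in 11.4. The SAP gives no SD, correlation or expected effect for change in LAZ, so there is no figure to reproduce and the values below are assumptions.

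**Step 1: closed form for the simplest case** (one coefficient, model 2 only, no true effect). Let ρ be the correlation of baseline LAZ with change in LAZ. In standard-error units the unadjusted difference is u = ρZ₁ + √(1−ρ²)Z₂, and the shift on adjustment is ρZ₁. The rule fires if |ρZ₁| > 0.1|u|. Since u/Z₁ = ρ + √(1−ρ²)C, with C standard Cauchy,

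P(fire) = [atan(9|ρ|/√(1−ρ²)) + atan(11|ρ|/√(1−ρ²))]/π.

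For |ρ| = 0.3: √0.91 = 0.954, then [atan(2.830) + atan(3.459)]/π = (1.231 + 1.289)/3.142 = 0.80. For |ρ| = 0.1, 0.2 and 0.4 the result is 0.50, 0.71 and 0.86. Neither sample size nor SD enters: at zero effect a larger trial does not help.

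**Step 2: simulation of the full rule** (models 2–4, 322 per group, common true effect). WHZ correlates 0.1 with the outcome, and there are ten further candidate covariates, five of them with correlation 0.08. Entries are the percentage of trials in which the rule fires if any of the five coefficients counts; in brackets, if only one counts.

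| True effect (Z) | SD 0.6, ρ −0.2 | SD 0.7, ρ −0.3 | SD 0.8, ρ −0.4 |
|---|---|---|---|
| 0 | 99.9 (91) | 100 (94) | 100 (95) |
| 0.10 | 96 (60) | 98.5 (72) | 99.5 (82) |
| 0.15 | 79 (35) | 94 (57) | 98 (70) |
| 0.20 | 54 (20) | 82 (41) | 95 (57) |
| 0.30 | 16 (6) | 53 (16) | 78 (36) |
| 0.50 | 0.5 (0) | 6 (2) | 30 (8) |

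A less favourable case for the concern has LAZ SDs of 1.0 at 6 months and 1.1 at 18 months with correlation r = 0.85, which implies ρ of about −0.11. There the any-of-five rate is about 98–99% at zero effect, 57% in one run and 64% in another at 0.10 Z, and about 1% at 0.30 Z.

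**Step 3: familywise error under the null with Holm** (same simulation as step 2, plus a run with 258 per group).

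| Procedure | Familywise error |
|---|---|
| Unadjusted t-test | 3.8–4.7% |
| Model 2 fixed in advance | 3.7–4.7% |
| Model 4 | 3.7–4.5% |
| Most favourable of models 2–4 | 5.6–6.6% |
| Most favourable of models 1–4 | 5.8–7.0% |

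**Step 4: precision.** Var(change) = s₆² + s₁₈² − 2r·s₆·s₁₈, and the residual variance after adjusting for baseline is s₁₈²(1−r²). With equal SDs the ratio is (1+r)/2: 0.80 at r = 0.6, 0.875 at 0.75 and 0.925 at 0.85. With SDs 1.0 and 1.1 and r = 0.85: Var(change) = 1 + 1.21 − 1.87 = 0.340, adjusted = 1.21 × 0.2775 = 0.336, ratio 0.99. The gain is thus about 1–20% lower variance.

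**The case against.** The strongest defence is that the rule is written down in advance and applied while codes are masked. If firing is taken to mean model 4, error control is intact (3.7–4.5%). A t-test on change is valid in a randomised trial, so preferring baseline adjustment is a matter of efficiency. On the single-coefficient reading the rule fires much less often, and at 0.3 Z or more it is far from automatic.

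Most of this stands, and it limits the point. A reader might infer that the analysts can see the treatment effects and pick a model to suit. The documents do not support that: the interventions behind the codes are unknown until the amended SAP is agreed, so there is no ready way to steer towards a favourable comparison with control. A reader might also infer a large loss of precision. That needs equal SDs at both ages and a moderate correlation, neither of which the SAP gives. It also conflicts with the firing rates: if the rule nearly always fires, an adjusted analysis is nearly always presented, and models 2 and 4 already contain baseline LAZ.

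What the defence does not answer is that the text never says model 4, never says which coefficient, and cannot define a contrast against control under masked codes.

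**Conclusion.** The concern holds as a failure to fix the primary analysis. Sections 11.3 and 12.6 do not together identify one primary estimate, and analysts following both could report different primary p-values from the same data. The trigger carries little information near zero effect: it fires in about 98–100% of trials there and roughly 55–100% at 0.1 Z on the any-of-five reading. This region is relevant, since Appendix 7 later reports no statistically significant growth promotion, although that does not establish a zero effect.

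The harm to error control is modest: about 6–7% familywise, and only if the most favourable model may be chosen. All firing rates other than the closed form rest on assumed SDs, and every rate rests on an assumed correlation. The near-zero result held at every value tried; the rates at 0.2–0.3 Z vary widely. The precision gain from baseline adjustment is a secondary benefit.

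**What to change.** - **12.6:** delete the 10% rule. Name one primary model before any group-coded data are opened: linear regression of change in LAZ on group with baseline LAZ as covariate, and Holm over the five coefficients against control. Report the unadjusted t-test and model 4 as sensitivity analyses.
- **11.3 and Table 2:** replace the t-test with this model, and show the adjusted differences with their intervals and p-values.
- **12.4:** base confidence intervals for this outcome on the regression instead of the t-test.
- **12.5:** this section lists baseline LAZ as a possible effect modifier and offers only variables without interaction as covariates. State that baseline LAZ stays in the primary model whatever the interaction test shows.
- **11.4:** add baseline LAZ to the non-inferiority regression for consistency.
- **Appendix 1 section 7.6 and Appendix 2 section 6.6:** both refer back to the procedure in 12.6, so each needs its own named model.

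The cost is wording in these sections. Data and software stay the same, and simulated familywise error with the fixed model is 3.7–4.7%.
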